1.0 INVESTIGATOR'S RESPONSIBILITIES

The Investigator is responsible for the data collection and the reporting of the clinical study information. The Investigator is also responsible for ensuring that the clinical study is conducted in compliance with all requirements of the clinical study protocol and all requirements as determined by the Institutional Review Board (IRB)/Independent Ethics Committee (IEC).

3.0 GLOSSARY

CCF	Cleveland Clinic Foundation
DEXA	Dual-energy X-ray absorptiometry
FRAX	Fracture Risk Assessment Tool
GFR	Glomerular filtration rate
IEC	Independent Ethics Committee
IRB	Institutional Review Board
PI	Principle Investigator
PTH	Parathyroid hormone
RC	Research coordinator
ROC	Receiver Operating Characteristic
SD	Standard deviation
SST	Serum Separator Tube

4.0 OBJECTIVE

This enrollment protocol is an effort to evaluate the correlation between serum and urine values of the bone marker of interest to help establish accuracy of serum values compared to urine.

Data collected in this clinical study may also be used for scientific publication purposes, authored by the study investigators or by scientists collaborating with the study investigator(s), for the advancement of scientific knowledge on bone diseases.

5.0 OVERVIEW

5.1 Background

Osteoporosis is the most common metabolic disorder in the United States and it is estimated that approximately 19% of women and 4% of men over the age 50 years have underlying disease. This number is expected to continue to rise. A silent illness at first, once presenting with fractures, it can lead to increased morbidity, mortality, and decreased quality of life. It carries large financial and societal burdens. Direct annual medical costs are estimated to be approximately 17 to 20 billion dollars in the United States alone [1]. Therefore, it is important to accurately identify those at high risk.

The present gold standard to diagnose osteoporosis is the Dual-energy X-ray absorptiometry (DEXA scan) [2] with a diagnosis based on a T-score of -2.5 SD or below in those without history of fragility fracture. However, many individuals fracture despite having normal or only mildly reduced scores. There are also several barriers within the DEXA technology including accessibility, cost, accurate reference ranges for age and demographic groups that result in missing large groups of people at risk for osteoporosis. The Fracture Risk Assessment Tool (FRAX score) is one tool that identifies those at higher risk of fracture that may benefit from therapy [3]. It was designed and released in 2008 and has been a great asset in clinical practice in stratifying risk and guiding management of osteopenic patients. However, FRAX may miss many individuals that may benefit from therapy due to its limited inclusion criteria [4].

Bone markers have been shown to predict fracture risk in postmenopausal women independent of bone mineral density and may help identify high risk individuals. Amino-terminal cross-linking telopeptides of type I collagen (NTX) reflects osteoclastic bone resorption. NTX can be measured in both the serum and in urine.

The accuracy of the serum NTX is unclear. It may be less sensitive than urine NTX in detecting bone density changes [5]. The urine NTX overcomes circadian rhythm changes to bone density and is less sensitive to dietary collagen intake [6,7]. At present, urine markers need to be checked as a second void of the day which may be cumbersome for patients. Serum levels drawn with other bone labs would be

easier to obtain than second void urine collections. We would like to evaluate the correlation between serum and urine NTX in patients with osteopenia with no prior history of osteoporotic treatment. If the urine and serum markers are equivalent methods, serum levels would be preferred to identify high risk patients at risk of disease due to ease of collection.

5.2 Study Site

This is a prospective blood and urine collection study under the supervision of clinical researchers. Subjects will be enrolled at the CCF

5.3 Overall Study Design

This is a prospective specimen collection cohort study to evaluate the correlation between serum and urine values of the bone marker of interest, and their association with baseline DEXA scan measures and fracture risk within 6 months.

Study samples will be obtained longitudinally. One collection of both serum and urine collection will be obtained. The urine will be collected as second void of day and at the same time the blood collection is drawn. Study will continue for a period or 1 year, with plan to enroll around 40 subjects.

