5.6 Required Information

This section lists the main information that will be collected for each subject by the Principal Investigator (or designee). Data will be captured in RedCap and will adhere to the data management plan as outlined in section 6.0.

At enrollment:

- Demographics
- Age and Gender
- Date of osteopenia diagnosis
- Bone mineral density and T-score values of latest DEXA scan
- Medical history; including history of any relevant concomitant conditions per CRF

- Date and time of blood draw and urine collection
- Calcium supplementation, duration and dosing
- Vitamin D supplementation, duration and dosing
- Laboratory such as:
 - Vitamin D level
 - PTH level
 - Calcium level
 - Alkaline phosphatase level
 - Creatinine level
 - GFR

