5.10 Statistical Analyses

Pearson or Spearman correlations will be used to measure the association between serum and urine markers. Similar correlation measures will be used to measure associations with DEXA scan results, and Comparisons of the correlations were performed using the cocor package in R software (version 4.0;

Vienna, Austria) using the methods by Meng, Rosenthal, and Rubin (1992) to compare the correlations and calculate 95% confidence intervals for their difference. As an exploratory analysis, associations between serum and urine levels with fracture risk will be evaluated using two-sample t-tests and, if feasible, ROC analyses will be used to compare the predictive ability of each marker. If the number of fractures is small, this analysis will not be performed. If the follow-up through 6 months cannot be measured consistently across patients, alternate methods including time to event analysis may be used to account for differential follow-up.

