5.11 Sample Size Justification

The primary sample size calculation was based on the ability to detect a moderate correlation ($r=0.5$) between serum and urine levels. With 40 patients, there will be 90% power to detect moderate correlations based on a two-sided test of the Fisher's Z test of the Pearson correlation (Image 1). Power calculations were performed using SAS software (version 9.4; Cary, NC). (8)

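### Does naming 6-month fracture risk in section 5.3, with no number behind the drop rule in 5.10, call for a change to the plan?

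*Combined protocol and SAP*

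**What the plan says.** Section 4.0 gives one aim, the serum-urine correlation, "to help establish accuracy of serum values compared to urine". It mentions neither fracture nor DEXA.

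Section 5.3, the design overview, adds "their association with baseline DEXA scan measures and fracture risk within 6 months" with no ranking and no condition. On size and duration it says: "Study will continue for a period or 1 year, with plan to enroll around 40 subjects".

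Section 5.10 is specific: "As an exploratory analysis, associations between serum and urine levels with fracture risk will be evaluated using two-sample t-tests". ROC analysis is to be used only where feasible. Then: "If the number of fractures is small, this analysis will not be performed". It also foresees uneven observation ("If the follow-up through 6 months cannot be measured consistently across patients") and names time-to-event analysis as an alternative.

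On sizing, section 5.11 states: "The primary sample size calculation was based on the ability to detect a moderate correlation". Fracture plays no part in it.

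Section 5.6 introduces its data list with "This section lists the main information that will be collected for each subject". The items shown are collected at enrolment, and no fracture outcome appears among them. Section 5.9 adds that results of standard-of-care procedures will be collected.

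**The concern.** Read in order, the sections give the fracture question three different standings: absent in 4.0, a plain purpose in 5.3, and exploratory and conditional in 5.10. Someone who stops at 5.3 would expect a fracture result.

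The drop rule also turns on the word *small*, with no count attached. If a handful of fractures occurred, the decision to run a t-test or ROC comparison could be made after the data were seen. At such counts, large AUCs come easily by chance.

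The readable text gives no fracture definition, no 6-month ascertainment and no enrolment window. If the one year includes follow-up and enrolment runs late, some patients will have less than 6 months. At stake would be a spurious claim that one marker predicts fracture better than the other.

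**Working it through.** **The plan's own figure.** Section 5.11 claims 90% power for r = 0.5 with 40 patients, two-sided. Taking alpha as 0.05 (not stated there), power = Φ(atanh(0.5) × √37 − 1.960) = Φ(0.5493 × 6.083 − 1.960) = Φ(1.381) = 91.6%. The claim reproduces, and it concerns the serum-urine correlation only.

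**Expected fractures.** Forty patients for 6 months is 40 × 0.5 = 20 person-years. With no rate in the documents, I assume 0.5% to 5% per year. The upper end is generous, because section 5.5 excludes prior fracture, high-risk medication and many conditions that raise fracture risk. Poisson, mean = rate × 20:

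| Rate per year | Mean | P(0) | P(1–4) | P(2–4) |
|---|---|---|---|---|
| 0.5% | 0.10 | 90.5% | 9.5% | 0.5% |
| 1% | 0.20 | 81.9% | 18.1% | 1.8% |
| 3% | 0.60 | 54.9% | 45.1% | 12.2% |
| 5% | 1.00 | 36.8% | 62.9% | 26.1% |

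P(5 or more) is at most 0.4%.

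**What the analysis could show at those counts.** The Hanley-McNeil standard error for an AUC of 0.70 with 40 patients is 0.213 at two fractures, 0.153 at four and 0.103 at ten. Multiplied by 1.96, the half-widths are 0.42, 0.30 and 0.20. The first puts the upper limit at 0.70 + 0.42 = 1.12, which is impossible. It shows only that the approximation has broken down and nothing can be estimated there.

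**Chance of a misleading AUC.** Suppose neither marker is related to fracture and the serum-urine correlation is 0.5. In simulation (50,000 samples of 40), at least one marker reaches an AUC of 0.8 or more with probability 0.313 at one fracture, 0.158 at two, 0.083 at three and 0.042 at four. The first value can be checked: with one fracture, AUC is at least 0.8 when the patient ranks in the top 8 of 40, so 0.20 per marker. Two markers give 0.40 less the overlap.

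Weighted by the Poisson probabilities:

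- 5% per year, one to four fractures: 0.368 × 0.313 + 0.184 × 0.158 + 0.061 × 0.083 + 0.015 × 0.042 = 0.150.
- 0.5% per year: 0.0905 × 0.313 + 0.0045 × 0.158 = 0.029.

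The single-fracture term supplies 0.115/0.150 = 77% of the first and 0.0283/0.029 = 98% of the second. One fracture is small on any ordinary reading. The fracture group would have no variance of its own, so an unequal-variance t-test could not be computed. Leaving that term out gives 0.035 and 0.0007, that is 3.5% and 0.1%.

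**Follow-up.** If the one year includes follow-up and entry is uniform, the share reaching 6 months is 6/6 when enrolment closes at month 6, 6/9 at month 9 and 6/12 at month 12. In the last case half the patients have 6 months and the rest average 3. That is 40 × 4.5/12 = 15 person-years, or 0.075 to 0.75 expected fractures. Short follow-up makes the drop rule more likely to apply.

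**Outside the assumed range.** At a 6-month risk of 5%, twice the top of the range above, the binomial gives 2 expected fractures, P(2 or more) = 60% and P(5 or more) = 5%. At 10%, P(5 or more) = 37%. Even with five fractures against 35 without, the t-test needs a standardized difference of about 1.37 for 80% power. With two against 38 it needs about 2.09.

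**The case for a change.** The strongest case for acting is that a rule without a number is not a rule fixed in advance. Within the assumed range, if any fracture occurs the count almost certainly falls between one and four, where *small* must be interpreted. The ROC condition and the time-to-event alternative add further open choices. A few sentences would close all of them, with no added visit, sample or patient.

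It is true that the text sets no count and that 5.3 lacks the exploratory label. It does not follow that the study is exposed. A one-sentence overview followed by a more specific analysis section is normal drafting. The silence of 4.0 says little, since 4.0 also omits the DEXA association, which 5.10 plans to analyse.

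Nor would a number gain much. Ten fractures, for example, has probability of about 1 in 10 million at the highest assumed rate, so that threshold amounts to deletion. Ten expected fractures would need 10/(0.05 × 0.5) = 400 patients at 5% per year, or 10/(0.005 × 0.5) = 4,000 at 0.5%. Any threshold that could be met with 40 patients would let through an analysis that cannot inform.

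The definition and ascertainment of fracture may be in the case report form or the figure, neither of which is visible, or may come through the standard-of-care results in 5.9. Their absence from the readable text is weak evidence that they are missing.

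**Conclusion.** No change is needed. The wording of 5.3 is looser than that of 5.10, but 5.10 controls the analysis: it labels the fracture comparison exploratory, makes ROC conditional, withdraws the whole analysis when fractures are few and provides for uneven follow-up. With 0.1 to 1.0 expected fractures, a sensible analyst will not run it.

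The residual risk, two to four fractures together with a chance AUC of 0.8 or more, is 0.1% to 3.5%. It becomes a reported result only if the team also reads those counts as not small and ROC as feasible. The figure rests on an assumed rate of 0.5% to 5% per year, full 6-month follow-up of 40 patients, a serum-urine correlation of 0.5 and no true association with fracture. A much higher fracture rate would bring the undefined word into play more often, but the result would still be exploratory and imprecise. The serum-urine correlation, its 90% power and the study's main conclusion do not depend on any of this.

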5.4 Subject Enrollment

Subjects will be enrolled prospectively, under Institutional Review Board (IRB) approval and patient informed consent. Enrollment will include patients diagnosed with osteopenia on DEXA scan who have not been on any medical therapy in the past. Recruitment will occur via phone, mail, virtual or in-office visit. Subjects will be consented in an office visit. Subjects will be identified either during an in-office visit, referral by colleague or via ICD code EPIC inquiry.

5.5 Inclusion and Exclusion Criteria

Subject Inclusion criteria

- Consent to participate in the study
- Participants limited to subjects in the CCF
- Age between and inclusive of 18 and 85 years of age
- No gender exclusion
- Patients diagnosed with Osteopenia on DEXA scan who have not been on any medical therapy in the past
- Presence of normal vitamin D levels, kidney function, and parathyroid hormone levels (per our reference ranges)

Sample Inclusion Criteria

- Serum sample collected in Serum Separator Tubes (SST) Gold tube and urine sample collected in clean container
- Samples to be collected only at a CCF Laboratory based on standard of care for the CCF
- Samples to be collected at the same time of day. Urine NTX will be collected as the second void of the day

Subject Exclusion criteria

- Prior history of medical therapy for osteopenia
- Prior radiation therapy
- Prior history of bone fracture
- History of high risk medication associated with increased risk of fracture
- Presence of abnormal vitamin D levels, kidney function, and parathyroid hormone
- Pregnancy status (verbal)
- Those with medical co-morbidities that increase the risk of fracture will be excluded and these include but are not limited to: rheumatoid arthritis, ankylosing spondylitis, psoriatic arthritis, diabetes mellitus, hyperparathyroidism, chronic kidney disease, pituitary disease, multiple myeloma, leukemia, lymphoma, thalassemia major, HIV/AIDS, malabsorption, Inflammatory bowel disease, chronic obstructive pulmonary disease, hypogonadism, chronic liver disease, untreated hyperthyroidism, and those with chronic immobility

Sample Exclusion Criteria

- Grossly hemolyzed (red) or turbid samples
- Samples with visually detected microbial contamination
- Sample not handled or stored as per sample handling instructions, which will be provided to the study sites at the time of the study initiation visit
- Urine sample that is not collected as second void of the day

5.6 Required Information

This section lists the main information that will be collected for each subject by the Principal Investigator (or designee). Data will be captured in RedCap and will adhere to the data management plan as outlined in section 6.0.

At enrollment:

- Demographics
- Age and Gender
- Date of osteopenia diagnosis
- Bone mineral density and T-score values of latest DEXA scan
- Medical history; including history of any relevant concomitant conditions per CRF

- Date and time of blood draw and urine collection
- Calcium supplementation, duration and dosing
- Vitamin D supplementation, duration and dosing
- Laboratory such as:
 - Vitamin D level
 - PTH level
 - Calcium level
 - Alkaline phosphatase level
 - Creatinine level
 - GFR

5.7 Sample Collection

- Consent subjects prior to blood draw and urine collection
- Laboratory tests will only be collected at CCF laboratory facilities per CCF standard of care
- The serial number labels should be affixed to each collection tube or container prior to the collection
- Patient samples will be serum from SST tubes Gold tubes and urine test from clean container. CPT code 82523
- Standard venipuncture must be done in accordance with institutional standards and requirements to collect whole blood
- A 2 mL SST tube of whole blood will be collected at study enrollment onset
- Standard urine collection will be done in accordance with institutional standards. The urine collection will be second void of the day
- A 5 mL clean container of second void of the day urine will be collected at study enrollment onset

5.8 Sample Handling

Will be handled per CCF laboratory standards

5.8.1 Stability

The urine and serum sample can be kept at ambient temperature for 1 day, if refrigerated for 7 days and if frozen for 14 days

5.9 Standard of Care Assessments

The study will collect the results of any procedures performed as per standard of care.

[figure not shown]
5.10 Statistical Analyses

Pearson or Spearman correlations will be used to measure the association between serum and urine markers. Similar correlation measures will be used to measure associations with DEXA scan results, and Comparisons of the correlations were performed using the cocor package in R software (version 4.0;

Vienna, Austria) using the methods by Meng, Rosenthal, and Rubin (1992) to compare the correlations and calculate 95% confidence intervals for their difference. As an exploratory analysis, associations between serum and urine levels with fracture risk will be evaluated using two-sample t-tests and, if feasible, ROC analyses will be used to compare the predictive ability of each marker. If the number of fractures is small, this analysis will not be performed. If the follow-up through 6 months cannot be measured consistently across patients, alternate methods including time to event analysis may be used to account for differential follow-up.

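### Section 5.10 compares serum NTX directly with urine NTX by a correlation only, with no measure of error in the individual patient and no criterion for the accuracy aim in 4.0

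*Combined protocol and SAP*

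**What the plan says.** The objective in section 4.0 is to "evaluate the correlation between serum and urine values of the bone marker of interest to help establish accuracy of serum values compared to urine". Correlation is the means and accuracy is the aim.

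Section 5.1 gives the reason: "The accuracy of the serum NTX is unclear". It then states the intended use: "If the urine and serum markers are equivalent methods, serum levels would be preferred to identify high risk patients".

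For serum directly against urine, section 5.10 plans one thing: "Pearson or Spearman correlations will be used to measure the association between serum and urine markers". Its other analyses are:

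- DEXA: "Similar correlation measures will be used to measure associations with DEXA scan results", with a comparison of the markers' correlations by the Meng-Rosenthal-Rubin method and a 95% CI for the difference.
- Fracture: exploratory t-tests and, where feasible, ROC curves. A condition applies: "If the number of fractures is small, this analysis will not be performed".

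Section 5.11 sizes the study at 40 patients for 90% power to detect r=0.5 with a two-sided Fisher z test. No section gives a prediction error, a cut-off with sensitivity or kappa against urine, an equivalence margin, or a correlation that would count as adequate.

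**The concern.** Replacing urine by serum to pick out high-risk patients is a decision about individuals. It turns on how far a patient's urine value could lie from what the serum value suggests. A correlation coefficient bears on this only on a standardised scale. It does not give the error in urine units, and the plan names no value of r that would suffice.

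The other analyses in 5.10 do not fill the gap. Two markers can correlate similarly with bone density and still disagree about a given patient. The ROC analysis takes fracture, not urine NTX, as its outcome. It is also exploratory and may be dropped, which is a realistic prospect with about 40 patients, prior fracture excluded (5.5) and a 6-month window (5.3).

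Followed exactly, the plan would report an association and leave the accuracy question in 4.0 without a basis for an answer.

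**Working it through.** **Inputs.** From 5.11: n=40, r=0.5, two-sided Fisher z test, 90% power. Assumed: null correlation 0 and alpha 0.05 (not in the readable text; Image 1, which is not shown, may give them), bivariate normality, and both results available for all 40 patients.

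**1. The plan's own figure.** The SE of Fisher's z is 1/√(40−3) = 0.1644, and atanh(0.5) = 0.5493. Power = Φ(0.5493/0.1644 − 1.96) = 0.916. The same formula needs 38 patients for 90%. The stated 90% reproduces, and the sample-size arithmetic is not in question.

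**2. Smallest significant correlation.** tanh(1.96 × 0.1644) = 0.31. The result depends on alpha. At two-sided 0.01 it would be tanh(2.576 × 0.1644) = 0.40, but power would then be Φ(0.5493/0.1644 − 2.576) = 0.78, which does not match the stated 90%. An alpha of 0.05 is the better fit.

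**3. Precision at an observed r=0.5.** Pearson: tanh(0.5493 ± 0.3222) = 0.22 to 0.70. Spearman, with variance (1 + r²/2)/(n − 3): 0.20 to 0.71.

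**4. What r means for one patient.** For a regression of urine on serum fitted to 40 patients, the 95% prediction half-width in urine SD is

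t(0.975, 38) × √[(1 − r²) × 39/38] × √[1 + 1/40 + d²/39],

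where d is the distance of the serum value from its mean in serum SD. Without serum, the half-width is t(0.975, 39) × √(1 + 1/40) = 2.05.

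| Observed r | d | Half-width (urine SD) |
|---|---|---|
| no serum result | – | 2.05 |
| 0.31 | 0 | 1.97 |
| 0.5 | 0 | 1.80 |
| 0.5 | 2 | 1.89 |
| 0.9 | 0 | 0.91 |

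At r=0.5 and the mean serum value, the limits are 1 − 1.798/2.048 = 12% narrower than with no serum result. At the smallest significant r they are 1 − 1.973/2.048 = 4% narrower.

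**The case against.** The strongest reply is that the documents promise little. Section 4.0 says only that the correlation should help establish accuracy. Section 5.1 states the aim as to "evaluate the correlation between serum and urine NTX in patients with osteopenia", and 5.3 does not mention accuracy. Equivalence appears only in a conditional background sentence. Sections 5.10 and 5.11 analyse and power the stated correlation. All of this stands, and it keeps the point small.

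A reader might infer that the sponsor will read a significant r as equivalence, or that r=0.5 is a success threshold. The documents support neither: no such decision rule is written, and 0.5 is only the value the study is powered to detect. Nor does the plan lack every other comparison of the markers. The DEXA comparison and the conditional ROC analysis bear on the choice between them, though neither measures serum against urine.

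A second reply is that prediction limits in SD units merely restate r and n. That is correct, so they are not evidence of a separate defect; they show what a given r implies for one patient. What r cannot supply is the error in urine units.

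A third is that a high versus not-high classification has no anchor in the documents, which define no NTX cut-off, and would be noisy at n=40. This also stands. Such a table should be optional, descriptive and tied to an existing laboratory limit. Likewise, the documents give no NTX units for either specimen, so they do not support a demand for limits of agreement on raw values. A regression does not need a common scale.

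**Conclusion.** The point holds for serum measured directly against urine. The plan's only such analysis is a correlation, and nothing in it says what result would help establish accuracy or support preferring serum. A correlation that is significant at n=40, or equal to 0.5, is compatible with serum being a poor substitute for urine in the individual patient: at r=0.5 the prediction limits shrink only from ±2.05 to ±1.80 urine SD.

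This is a low-cost improvement to the analysis section, not an error in the design or the power calculation. The significance threshold rests on the assumed null of 0 and alpha of 0.05, and the prediction limits on approximate normality and 40 complete pairs. That 5.10 has no other serum-against-urine analysis rests on none of these.

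**What to change.** In 5.10:

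1. Report the serum-urine correlation with its 95% CI, described as a measure of association.
2. Add a regression of urine on serum with 95% prediction limits in urine units, on the log scale and back-transformed if values are skewed.
3. State that a correlation significantly above zero will not by itself be read as accuracy or equivalence, and that such a conclusion needs a criterion the sponsor sets before analysis.
4. Optionally, and only if laboratory NTX limits exist, add a descriptive cross-classification of high versus not high with exact CIs.

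In 5.11, add the expected precision for the Pearson correlation: 95% CI 0.22 to 0.70 at r=0.5 with n=40.

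The cost is wording and a few lines of code. The paired values come from the sampling already planned in 5.3 ("One collection of both serum and urine collection will be obtained"), so no new patients, samples or procedures are needed. The downside is imprecision. For the optional table, if 13 patients were urine-high and serum found 7, the exact 95% CI for sensitivity would be 25% to 81%; with 13 of 20 it would be 41% to 85%. The study may be able to conclude only association, and the added estimates would then mainly inform a later study.

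### Does the serum-versus-urine comparison against DEXA need a change because 40 osteopenia-only patients give it little power?

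*Combined protocol and SAP*

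**What the plan says.** Section 4.0 sets the objective as the correlation between serum and urine values of the bone marker. Section 5.3 adds association with baseline DEXA measures, "with plan to enroll around 40 subjects". Section 5.10 then says: "Similar correlation measures will be used to measure associations with DEXA scan results, and Comparisons of the correlations were performed using the cocor package", and specifies the Meng, Rosenthal and Rubin method with 95% confidence intervals for the difference. That method compares dependent correlations, so serum-DEXA against urine-DEXA is the likely target.

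The cohort is defined in section 5.5: "Patients diagnosed with Osteopenia on DEXA scan who have not been on any medical therapy in the past". Section 5.6 collects "Bone mineral density and T-score values of latest DEXA scan", with no skeletal site named. On sample size, section 5.11 says: "The primary sample size calculation was based on the ability to detect a moderate correlation", meaning r = 0.5 between serum and urine, with 90% power at 40 patients. It makes no power statement about DEXA.

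The motivation is in section 5.1. Of serum NTX it says: "It may be less sensitive than urine NTX in detecting bone density changes". It then says: "If the urine and serum markers are equivalent methods, serum levels would be preferred to identify high risk patients". The fracture analysis in section 5.10 is exploratory and conditional: "If the number of fractures is small, this analysis will not be performed".

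**The concern.** Restricting the cohort to osteopenia narrows the spread of DEXA values. If NTX tracks bone density over the full range, both marker-DEXA correlations shrink inside the cohort, and so does the gap between them. The 40 patients were not chosen with that gap in mind.

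This is also the only planned non-exploratory analysis that sets the two markers against a bone measure. Section 5.1 prefers serum if the methods are equivalent, and section 5.10 offers a difference test with no equivalence margin. A test that usually returns no significant difference, even when urine is clearly better, could then be taken as support for serum. With no site named, several sites might be tested. For truly equal markers, simulation puts the chance of at least one false difference at 8.5-9.4% with two sites and 12.1-13.3% with three.

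**Working it through.** **1. The plan's own figure.** Inputs from section 5.11: r = 0.5, N = 40, two-sided Fisher z test. The documents state no alpha; 0.05 is assumed, in line with the 95% intervals.

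Power = Φ(atanh(0.5) × √(N − 3) − 1.96) = Φ(0.5493 × √37 − 1.96) = Φ(1.381) = 91.6%. The stated 90% is reproduced (38 patients would suffice).

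**2. The Meng comparison, taking 0.5 (urine) and 0.2 (serum) as correlations inside the cohort.** These two values are assumptions. With r_x the serum-urine correlation:

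- z = (z₁ − z₂) × √[(N − 3) / (2(1 − r_x)h)]
- h = (1 − f·r̄²) / (1 − r̄²), where r̄² is the mean of the two squared correlations
- f = (1 − r_x) / (2(1 − r̄²)), capped at 1

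At r_x = 0.5:

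- z₁ − z₂ = 0.5493 − 0.2027 = 0.3466
- r̄² = (0.25 + 0.04)/2 = 0.145
- f = 0.5/(2 × 0.855) = 0.292
- h = (1 − 0.292 × 0.145)/0.855 = 1.120
- z = 0.3466 × √(37/1.120) = 1.99

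Power = Φ(1.99 − 1.96) = 51% (53% by simulation). Analytically it is 72% at r_x = 0.7 and 99% at 0.9. At r_x = 0.5, 80% power needs N = 77.

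**3. The same values taken as full-range correlations, then restricted.** Further assumptions: source T-score mean -1 and SD 1, with the analysed site cut to -2.5 to -1.0. Section 5.1 gives the -2.5 limit; the -1.0 limit is not in the documents. The SD ratio after the cut is u = 0.406. With r′ = r·u / √(1 − r² + r²u²):

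- urine: 0.203/√0.791 = 0.228
- serum: 0.081/√0.967 = 0.083
- Fisher z gap: 0.232 − 0.083 = 0.149

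Simulated power at N = 40:

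| Situation | r_x 0.5 | r_x 0.7 | r_x 0.9 |
|---|---|---|---|
| 0.5 v 0.2 inside the cohort | 53% | 76% | about 100% |
| Cut to -2.5 to -1.0 | 13% | 21% | 73% |
| Cut to -2.5 to -0.5 | 20% | 32% | – |
| Cut to -2.5 to 0 | 27% | 44% | – |

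Varying the source distribution and the number of sites moves the second row to about 12-15% at r_x = 0.5 and 73-84% at 0.9.

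**4. What the planned interval would show.** At r_x = 0.5 the half-width on the Fisher z scale is 1.96/√(37/1.120) = 0.34, and it is about the same after restriction. If the observed difference were zero, the interval would run from about -0.34 to +0.34. It would contain the restricted gap of 0.15 and reach almost to the unrestricted gap of 0.35. The imprecision would be visible in the reported result.

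**5. Whether a remedy gains anything.** Suppose serum were called as good as urine when the upper 95% limit for the gap in |r| (Fisher z, mean T-score over sites) fell below 0.20. In simulations with the lowest site between -2.5 and -1.0:

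- Truly equal markers pass in only 18-23% / 26-35% / 62-75% of trials at r_x 0.5 / 0.7 / 0.9.
- When full-range truth is 0.5 v 0.2, serum is still wrongly passed in about 2-5% / 4-9% / 9-20%, because a serum correlation of the wrong sign is credited to serum.
- With two sites correlated 0.75, the true gap in that case is 0.19, already inside the margin.
- Averaging T-scores raises power to 20-31% at r_x = 0.5 if the gap is common to all sites, but gives 8-12%, against 54-87% at the affected site, if the gap is at one site only.

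**The case for a change.** The strongest case for a change is that it costs a few sentences: name one DEXA variable, add a reading rule, and state in section 5.11 that the 40 patients were not sized for this comparison. Even at the favourable reading, power is only about 53% at a serum-urine correlation of 0.5, so a null result cannot show that the markers are interchangeable.

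That last statement stands. The rest carries less weight:

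- **The low figures are conditional.** The 12-15% needs a source distribution, an upper T-score limit and full-range correlations, none of which the documents give. The serum-urine value of 0.5 is an effect the study should be able to detect, not a forecast.
- **Power is lowest where equivalence is least credible.** At a serum-urine correlation of 0.5 the markers share 0.5² = 25% of their variance, and the main analysis would itself argue against equivalent methods. At 0.9 they share 81%, and the comparison has reasonable power even after restriction.
- **The restriction is the target population.** Section 5.1 asks about untreated patients with osteopenia, so the correlation inside that group is the quantity of interest.
- **The misreading is not in the plan.** Section 5.1 gives motivation, not a decision rule, and section 5.11 already ties its calculation to serum and urine levels.

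**Conclusion.** The concern does not call for a change. The DEXA comparison is imprecise at 40 patients: about 53% power for 0.5 v 0.2 inside the cohort at a serum-urine correlation of 0.5, and about 12-15% if those are full-range values under the assumed cut at -2.5 to -1.0. But the plan promises no power for it, and the objective and sample size rest on the serum-urine correlation, which uses no DEXA variable. The interval already required, about ±0.34 on the Fisher z scale at that serum-urine correlation, would tell any reader that equivalence has not been shown.

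The unnamed site and measure are missing detail that an analyst can settle before examining marker results, given that section 5.6 collects both bone mineral density and T-scores. The choice between a single site and an average, and of any margin, is a trade-off: each option tested helps in one scenario and loses in another, and none makes 40 patients conclusive. The exact power figures rest on the assumed correlations, T-score distribution and two-sided 0.05 level; the conclusion does not depend on which of them is right.
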